17.1.6 Visual Acuity Testing

Best-corrected VA is measured at all trial visits using standard charts, lighting, and procedures. Best correction is determined by careful refraction at that visit according to the standard

protocol for refraction as described in the previous section.

17.1.7 Visual Acuity Charts

Chart 1 is used for testing the VA of the right eye; Chart 2 for testing the left eye; and Chart R for testing refraction only. Patients should not be allowed to see any of the charts before the examination.

17.1.8 Visual Acuity Lane and Visual Acuity Box

A distance of **4 meters** is required between the subject's eyes and the VA chart. With the box light off, not more than 15 foot-candles of light (161.4 Lux) should fall on the center of the chart. To measure the amount of light, the room is set up for VA testing, but with the box light off. The light meter is placed at the fourth line from the top of the chart, with its back against the chart and the reading is taken. If more than one lane is available for testing VA, the VA of an individual subject should be measured in the same lane at each visit, if possible. If different lanes are used to test VA, they must each meet the same standards.

Retro-illuminated ETDRS charts are used in this trial. The illuminator box will be either wall-mounted or mounted on a stand manufactured by the Lighthouse Low Vision Services. The light box should be mounted at a height such that top of third row letter is 49 ± 2 inches from floor.

The VA light box is equipped with two General Electric Cool Daylight 20-watt fluorescent tubes and a ballast which partially covers the tubes. Because the illumination of fluorescent tubes diminishes by 5 percent during the first 100 hours and by another 5 percent during the next 2000 hours, new tubes should be kept on for 4 days (96 hours) continuously, and should be replaced once a year.

A sticker should be placed on the back of the light box, indicating the date on which the present tubes were installed. A spare set of burned in bulbs should be available on site.

Each tube is partly covered by a 14-inch fenestrated sleeve, which is open in the back. This serves as a baffle to reduce illumination. Each sleeve should be centered on the tube with the opening towards the back.

17.1.9 Corrected Visual Acuity Measures

- As a reminder, Charts 1, 2, and R are used for testing the right eye, left eye, and refraction, respectively. Patients should not see the charts until the test begins.
- All eyes must be tested at 4 meters first, even if the refraction was performed at 1 meter.

- The subject should be seated comfortably directly in front of the chart so that the eyes remain at the 4 meter distance. Testing always begins with the right eye. Occlude the subject's left eye. A folded tissue or eye pad lightly taped over the eye behind the trial frame serves as an effective occluder that allows eccentric fixation without inadvertent use of the covered eye. After testing the right eye, occlusion of the right eye should be done BEFORE Chart 2 is put up for testing the left eye.
- The lens correction from the subjective refraction should be in the trial frame worn by the subject.
- The subject is asked to read the letters slowly, approximately one letter per second. The subject should be told that only one chance is given to read each letter on the chart. If the subject is unsure about the identity of the letter, then the subject should be encouraged to guess.
- The subject should begin by reading the top line of the chart and continue reading every letter on each smaller line, from left to right on each line. The examiner circles every correct letter read and totals each line and the whole column (0 if no letters are correct) on the data collection form. An X is put through letters read incorrectly. Letters, for which no guess was attempted, are not circled. When a subject reaches a level where he/she cannot guess, the examiner may stop the test provided that the subject has made errors on previous guesses, which is a clear indication that the best VA has been obtained.
- When a subject cannot read at least 20 letters on the chart at 4.0 meters, the subject is tested at 1.0 meter. The distance from the subject to the chart should be measured again using the rigid one meter stick. The distance is measured from the outer canthus to the center of the fourth letter (right eye) or the second letter (left eye) of the third line of the chart. The spherical correction in the trial frame should be changed by adding +0.75 to correct for the closer test distance. The subject may fixate eccentrically or turn or shake his/her head to improve VA. If this is done, the examiner must ensure that the FE remains occluded both centrally and peripherally and that the subject does not move forward in the chair. Particular care should be taken to make sure the subject does not move forward when testing at 1 meter. The subject should be reminded to blink.
- The examiner should not tell the subject if a letter was identified correctly. The subject may be encouraged by neutral comments, such as "good", "next", and "OK".
- The examiner should not stand close to the chart during testing. Attention should be focused on the subject and the data collection form. If the subject has difficulty locating the next line to read, the examiner may go up to the chart and point to the next line to be read, but then must move away from the chart.

- When it is possible to measure the VA of the eye at 4.0 meters (i.e. 20 or more letters read at 4 meters), the VA score for that eye is recorded as the number of letters correct plus 30. The subject gets credit for the 30 1M letters even though they did not have to read them. Otherwise, the VA score is the number of letters read correctly at 1.0 meter plus the number, if any, read at 4M. If no letters are read correctly at either 4.0 meters or 1 meter, then the VA score is recorded as 0.

17.1.10 Testing for Count Fingers Vision, Hand Motion Vision and Light Perception/No Light Perception Vision

If the subject's VA is so poor that he/she cannot read any chart letters when tested at one meter then the subject's ability to count fingers, detect hand motion, or have light perception should be evaluated.

Testing for Count Fingers Vision

In testing for count fingers vision, the examiner's hand holding 1, 2, or 5 fingers is held steady at a distance of two feet directly in front of the eye being examined. The FE is completely occluded with a patch on the face. A light should be shown directly on the hand from behind the subject. The examiner's fingers should be presented in random order and repeated 5 times. Eccentric fixation, if present, should be encouraged. If the subject correctly identifies three of the five presentations, then count fingers vision is noted. If not, then the subject must be tested for hand motion vision.

Testing for Hand Motion Vision

The examiner's hand with all fingers spread out should be extended two feet directly in front of the eye being examined. The FE should be occluded with a patch on the subject's face. A light should be shone directly on the hand from behind the subject. The examiner's hand should be moved in an up-and-down direction (vertically) or in a side-to-side direction (horizontally) at a constant speed of approximately one back and forth presentation per second. The subject is instructed that the examiner's hand will be presented and they will have to respond to the question: "What am I doing with my hand?" This should be repeated five times. Three out of five correct responses indicate that hand motion vision is present. If the subject does not correctly identify three of five presentations, then you must test for light perception.

Testing for Light Perception/No Light Perception Vision

Light perception should be tested with an indirect ophthalmoscope in a darkened room. The indirect ophthalmoscope light should be in focus at 1 meter with the rheostat set at maximum voltage. From that distance the beam should be directed in and out of the eye at least four times, and the subject should be asked to respond when he or she sees the light. If the

examiner is convinced that the subject perceives the light, vision should be recorded as “light perception”, if not, vision should be recorded as “no light perception”.

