The charts used for measuring distance VA must NOT be used for refraction. Refraction for each eye should be performed at 4 meters unless the subject's VA measured at 4 meters on the refraction chart (Chart R) is worse than 20/160. If VA is worse than 20/160 the eye is refracted at 1.0 meter. If during the refraction process at one meter, the subject is reading letters on the eighth line or lower, the refraction should continue at 4 meters. Whenever a subject cannot read any letters on the top line of Chart R at 1.0 meter the vision should be checked with a pinhole to see whether reduced vision is due, at least in part, to a larger refractive error. If there is no improvement with the pinhole, then the eye is exempt from refraction.

Subjective refraction as described below should be performed for corrected aphakic patients, including those with intraocular lenses. For uncorrected aphakic patients, a +10.00 diopter sphere should be added to the trial frame as the beginning approximate refraction.

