- c) If the subject prefers the negative (red) axis coincident with the cylinder axis, the total power of the correcting plus cylinder is reduced by 0.25 diopter. Repeat the process until the subject cannot choose one of the cross cylinder positions over the other. If the subject indicates a change that would introduce negative cylinder power, remove all cylinder power and continue testing for positive cylinder power at an axis 90° away from the previous axis. Otherwise go to Step 8d.
- d) If the subject prefers the positive (white) axis coincident with the cylinder axis, increase the power of the cylinder by 0.25 diopters and return to Step 8b. Otherwise proceed to Step 8e.
- e) When the subject feels that both positions are equally bad or good, and the cylinder power in the trial frame has changed by more than 0.50 diopter, return to Step 7c and re-adjust the axis if necessary. Otherwise, proceed to Step 9.

*Note: If the cylinder is changed by more than 0.50 diopter, the spherical equivalent should be maintained. (For each 0.50 **plus** CX increase, add -0.25 to the sphere, for each 0.50 **minus** CX increase, add +0.25 to the sphere).*

- 9. **Spherical Correction Refinement:** Recheck the power of the sphere by adding +0.25 and -0.25 spheres and changing the spherical power by 0.25 diopter increments of the appropriate sign until the subject cannot detect any improvement in vision. As a reminder, spherical testing should always begin and end with a plus lens.
- 10. Record the lens corrections obtained by subjective refraction for the right eye on the examination form in the section for VA measurements as the corrections obtained by protocol refraction for the right eye. If the corrective power was changed by more than 2 diopters from the starting refraction, confirm that the subject can read at least as well as the beginning approximate refraction. If not, then begin again at Step 1 and repeat the process.
- 11. Repeat the entire process (Steps 1-10) for the left eye and record the result on the examination form.

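### Appendix 17.1 does not convert a 1 m refraction for the 4 m acuity test, so read literally the poorest-seeing eyes carry a nominal 0.75 D too much plus at both test distances (minor)

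*Protocol*

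**What the plan says.** All the relevant steps are in Protocol Appendix 17.1.

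- **Refraction distance (17.1.3).** Refraction is at 4 m unless acuity on Chart R is too poor: "If VA is worse than 20/160 the eye is refracted at 1.0 meter". There is a way back. If during the 1 m refraction "the subject is reading letters on the eighth line or lower, the refraction should continue at 4 meters".
- **Recording (17.1.5, step 10).** "Record the lens corrections obtained by subjective refraction for the right eye on the examination form"; the left eye follows the same steps. The lens is recorded as found.
- **Acuity test at 4 m (17.1.9).** "All eyes must be tested at 4 meters first, even if the refraction was performed at 1 meter". For that test, "The lens correction from the subjective refraction should be in the trial frame worn by the subject".
- **Acuity test at 1 m (17.1.9).** "When a subject cannot read at least 20 letters on the chart at 4.0 meters, the subject is tested at 1.0 meter". On moving closer, "The spherical correction in the trial frame should be changed by adding +0.75 to correct for the closer test distance". No exception is made for an eye refracted at 1 m.
- **Score (17.1.9).** For an eye tested at 1 m, "the VA score is the number of letters read correctly at 1.0 meter plus the number, if any, read at 4M".
- **LLVA (17.1.11).** The same refraction is used, with a neutral density filter added.

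BCVA and LLVA are exploratory endpoints (Protocol 5.2). SAP 4.5 summarises the score and its change from baseline by cohort, and the Protocol synopsis rules out statistical inference.

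**The concern.** The closer-distance add assumes that the frame holds a lens found at 4 m. Section 17.1.9 acknowledges that some eyes were refracted at 1 m, yet gives no step to change their lens before the 4 m test and no exemption from the add at 1 m. Such an eye would be tested with too much plus at both distances, and both tests feed its score. Accommodation cannot clear excess plus.

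At stake is whether BCVA and LLVA in the worst-seeing eyes are truly best-corrected. An eye whose refraction distance changes between visits would also gain or lose some letters for optical reasons unrelated to its disease.

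**Working it through.** **1. Reproduce the plan's figure.** The focusing demand at distance d metres is 1/d dioptres: 1.00 D at 1 m and 0.25 D at 4 m. The difference is 1.00 − 0.25 = 0.75 D, which matches the add in 17.1.9.

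**2. Lens error under the text as written.** Let F be the far correction and assume no accommodation (Protocol 4.6 gives a mean age of 77 years in the pivotal studies). The ideal lens is F + 0.25 at 4 m and F + 1.00 at 1 m. Error is the lens in the frame minus the ideal lens.

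| Refraction distance | Lens at 4 m | Error at 4 m | Lens at 1 m after +0.75 | Error at 1 m |
|---|---|---|---|---|
| 4 m | F + 0.25 | 0.00 D | F + 1.00 | 0.00 D |
| 1 m, as written | F + 1.00 | +0.75 D | F + 1.75 | +0.75 D |
| 1 m, with −0.75 D before the 4 m test | F + 0.25 | 0.00 D | F + 1.00 | 0.00 D |

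**3. Precision of the 1 m refraction.** The chart in 17.1.12 refines a 1 m refraction in 1.00 D steps, that is, to about ±0.50 D. An individual eye would then be about 0.75 − 0.50 = +0.25 D to 0.75 + 0.50 = +1.25 D off. Below 20/400 the steps are 2.00 D with no refinement (about ±1.00 D), which gives −0.25 to +1.75 D. Rounding adds scatter around the 0.75 D shift but does not remove it.

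**4. Which eyes.** Assume a standard ETDRS chart: top line 20/200 at 4 m, hence 20/800 at 1 m, with 0.1 log unit and five letters per line. Line 8 at 1 m is then 800/10^0.7 ≈ 160, or 20/160. An eye that reads letters on that line goes back to 4 m refraction. The first chart level that keeps a 1 m lens is therefore 20/200. Eyes of 20/160 or better that are still tested at 1 m were refracted at 4 m, and for them the add is correct.

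**5. Size in letters.** The documents give no conversion, so this rests on assumptions. Two models were used, both with letters lost = 50 × log10(√(MAR² + B²)/MAR). MAR is the eye's own resolution limit in arcmin (10 at 20/200, 20 at 20/400).

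- *Model A, geometric blur.* B = k × pupil (m) × 0.75 × 3438, with pupil 2.5 to 4 mm and k = 0.5 to 0.65. The blur disc is 6.4 to 10.3 arcmin, so B runs from 0.5 × 6.4 ≈ 3.2 to 0.65 × 10.3 ≈ 6.7.
- *Model B, acuity limit.* 0.75 D alone is taken to limit a normal eye to between 20/30 and 20/100, so B = 1.5 to 5.

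| Acuity | Model A | Model B | Combined range |
|---|---|---|---|
| 20/200 | 1.1 to 4.0 | 0.2 to 2.4 | 0.2 to 4 letters |
| 20/400 | 0.3 to 1.2 | 0.1 to 0.7 | 0.1 to 1.2 letters |

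Example, model B upper end at 20/200: 50 × log10(√(100 + 25)/10) = 50 × log10(1.118) = 2.4.

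**6. Effect on change from baseline.** An eye refracted at 1 m at Month 1 and again later carries the same nominal offset both times, so it largely cancels. An eye that moves from 4 m to 1 m refraction goes from 0.00 to +0.75 D and picks up an artificial loss. An eye moving the other way picks up an artificial gain.

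**The case against.** The strongest reply is that actual mis-testing is not shown. Protocol 7.1 requires certified examiners and says the sponsor provides all necessary instructions, and 17.1.11 promises further LLVA procedures. The conversion may be in that material. This stands as a limit on the claim: the documents show a gap in the written procedure, not what sites did. It does not close the gap, because the appendix as written leads to the error.

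A second reply is that 0.75 D is smaller than the 1.00 D refinement step at 1 m. That is true for a single eye, but rounding goes both ways and the omission goes one way.

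A third is that this is one omission, not two errors. That is right: once the frame holds a 4 m lens, the add at 1 m is correct.

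A reader might also infer more than the documents support:

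- **Blur pushes eyes under the 20-letter cut-off.** A fourfold change of distance equals six chart lines, consistent with the 30-letter credit in 17.1.9, so line 8 at 1 m corresponds to line 2 at 4 m. An eye that keeps a 1 m lens reads nothing on that line and so reads about five letters at most at 4 m even in focus. It is already far below 20.
- **The loss should be taken at 20/160.** The models give larger values there, but 17.1.3 keeps eyes at that level on 4 m refraction.
- **It would trigger the acuity criteria in Protocol 10.3 or 12.3.** The range at 20/200 does not exceed the 5-letter change in 10.3, and that section says acuity change alone does not require imaging. A few letters cannot by themselves produce the 30-letter decrease in 12.3.

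**Conclusion.** The gap is real and minor. Read literally, Appendix 17.1 leaves an eye refracted at 1 m with a nominal 0.75 D too much plus at both test distances. That result needs only the protocol's own steps and the assumption of no accommodation.

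The effect on scores is less certain. Its direction is downward, and its size is about 0.2 to 4 letters at 20/200 and 0.1 to 1.2 at 20/400, under assumed pupil sizes and blur models that the documents do not supply. It shrinks as acuity worsens. The main consequence is a small bias in change from baseline for eyes that move between refraction distances; how many do so is not stated. With exploratory endpoints, descriptive summaries and a single treatment, the documents do not support calling it a material distortion of the BCVA or LLVA results, or a threat to the safety thresholds.

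**What to change.** Add one sentence to 17.1.9: when the refraction was performed at 1 m, add −0.75 D sphere to the trial frame before the 4 m test. The existing +0.75 D step for the 1 m test can then stay as it is, and the nominal error is 0.00 D at both distances. State in 17.1.11 that LLVA uses the same converted lens. Record the refraction distance on the examination form, so that eyes that moved between distances can be identified, and record the date of the change. If separate sponsor instructions already contain the conversion, the appendix should state it too.

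The cost is a short text change and a site memo, with no additional testing. The downside is a small upward step in the scores of affected eyes at the change-over, which is why the date needs recording.

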17.1.11 Procedures for Refraction and Vision Testing under Low Luminance

Once the subject has been refracted and had their vision measured under normal light conditions, a neutral density filter will be added to the trial frame and the ETDRS VA will be measured again using the same refraction noted above. Additional specification of the neutral density filter and procedures will be provided by the Sponsor.

17.1.12 Refraction Sequence Chart

Refraction Protocol Summary							
Vision with Best Correction (Refraction Distance)	Sphere		Cylinder			Sphere Refinement	
	Power (a)	Increment	Axis (b)	Power (c)	Increment	Power (d)	Increment
20/10 - 20/80 (4 meters)	+ .50 - .50	+ .50 - .50	.25 JCC	.25 JCC	+ .25 - .25	+ .25 - .25	+ .25 - .25
20/10 - 20/160 (4 meters)	+1.00 -1.00	+1.00 -1.00	.50 JCC	.50 JCC	+ .50 - .50	+ .50 - .50	+ .50 - .50
20/20 - 20/400 (1 meter)	+2.00 -2.00	+2.00 -2.00	1.00 JCC	1.00 JCC	+1.00 -1.00	+1.00 -1.00	+1.00 -1.00
<20/400 (1.0 meters)	+2.00 -2.00	+2.00 -2.00	No cylinder test			No refinement	

Sequence of Refraction: (a) - (d)

17.2 Intravitreal Administration Protocol

This protocol applies to avacincaptad pegol injections.

The injection volume for avacincaptad pegol 2 mg is 0.10 mL (100 µL).

Only an ophthalmologist who is experienced with IVT injections may perform the IVT injection.

In addition to the procedures outlined, any additional safety measures in adherence to specific institutional policies associated with intravitreal injections may be utilized.

New bottles of topical eye drops should be used for each patient at each visit.

NOTE: Prior to the IVT injection, direct ocular massage using a sterile cotton-tip applicator at the intended site of injection may be utilized at the Investigator's discretion. However, a paracentesis **MAY NOT** be performed **prior** to injection of the IVT drug.

NOTE: Pre-operative antibiotic drops are NOT recommended prior to the scheduled injection(s) of IVT drug. In addition, peri-operative and post-operative antibiotic drops are NOT recommended at the time of the procedure or after the procedure, respectively. However, if it is considered the standard of care at the individual institution, appropriate broad spectrum topical antibiotics may be prescribed for subject use at the discretion of the Investigator.

Before the Injection Day

- 1) If pre-operative topical ofloxacin, levofloxacin, or an antibiotic drop with comparable antimicrobial coverage therapy is ordered by the Investigator, the subject should be instructed to initiate the use of such antibiotic drops according to the regimen selected at the discretion of the Investigator. The antibiotic drops should be provided to the subject with clear instructions of how to use them at the visit immediately prior to each planned injection.

Preparation on the Day of the Injection

- 2) Within one hour prior to injection, topical 1% tropicamide (e.g., Mydracyl) and 2.5% phenylephrine (e.g., Neo-Synephrine) from new bottles should be applied topically to achieve adequate pupillary dilation. If 2.5% phenylephrine is not available, another dilating drop may be used at the discretion of the Investigator.
- 3) Injection preparation (for the following, new povidone-iodine bottles must be used and cannot be shared between patients):
 - a. Apply single use topical anesthetic drop(s) to the eye.

- b. Apply 2 to 3 drops of povidone-iodine to the injection site.
 - c. OPTIONAL: Apply 2 to 3 drops of povidone-iodine to the lower fornix and/or use sterile cotton-tipped applicators soaked in 5% or 10% povidone-iodine to swab the upper and lower eyelid margins and the upper and lower eyelashes.
- 4) Place a sterile eyelid speculum to stabilize the eyelids.
- 5) Consider additional anesthesia with the application of one or two cotton-tipped applicators soaked in topical anesthetic over the intended injection site for at least 30 seconds. Subconjunctival anesthesia (0.5 mL of 2% xylocaine without epinephrine subconjunctivally at the intended injection site) can be used if the Investigator believes that topical anesthetic is not sufficient to minimize discomfort. **Lidocaine gel is not permitted.**
- 6) Encourage the study participant to look superonasally (if injection site is inferotemporal) during the application of the povidone-iodine. Apply one of the following to the conjunctiva directly over and surrounding the intended injection site:
 - a. A cotton-tipped applicator soaked in 5% or 10% povidone-iodine.
 - b. A 10% povidone-iodine swab stick.
 - c. At least 3 drops of 5% povidone-iodine (at least enough to cover the intended injection site).
- 7) Allow 30 to 60 seconds for the povidone-iodine to be in contact with the injection site before injection.

NOTE: As indicated above, injection preparation must include the use of povidone-iodine either applied directly to the injection site using topical drops, a cotton-tipped applicator, or a swab stick. If a study participant experiences an adverse reaction to povidone-iodine, other approaches to limit the exposure of povidone-iodine may be permitted. However, **a study participant may not receive a study intravitreal injection without use of povidone-iodine directly to the injection site just prior to the injection.**

- 8) Sterilized calipers should be used to measure the injection site. The entry site of the needle for the IVT injection should be 3.0 to 3.5 mm from the limbus in aphakic/pseudophakic patients, and 3.5 to 4.0 mm in phakic patients.

NOTE: During the preparation and injection of the drug, Investigators, ancillary staff, and patients should refrain from talking. If talking becomes

absolutely necessary, the Investigator should face away from the bare needle and the injection site to avoid contamination of the needle and injection site. Wearing a mask during the preparation and injection of the study drug is optional.

Avacincaptad pegol 2 mg (0.1 mL injection volume) Injection Procedure:

- a. Use sterile gloves during preparation and administration of the injectable drug.
- b. Using aseptic technique, 0.2 mL of the avacincaptad pegol injection vial contents are withdrawn through a 5-micron filter needle attached to a 1-mL sterile syringe (supplied). Please see the study drug manual for appropriate withdrawal technique. The filter needle should be discarded after withdrawal of the vial contents and should not be used for intravitreal injection. The filter needle should be replaced with the sterile 30-gauge needle (supplied) for the intravitreal injection. The contents and any air bubbles should be expelled until the plunger tip is aligned with the line that marks mg 0.10 mL on the syringe for avacincaptad pegol 2 mg.
- c. Insert the drug into the vitreous cavity pointing toward the optic nerve via the pars plana. Once the needle is in place, continuous pressure should be applied to the syringe for approximately 10 seconds to assure slow, even delivery of all drug.
- d. As the needle is withdrawn, a sterile cotton tip applicator should be rolled over the entry site to minimize the risk of drug reflux. This should be held in place for a full 10 seconds.
- e. The eye can then be irrigated as per the typical practice pattern of the Investigator to minimize irritation from the aseptic procedure.
- f. Zero to five minutes following the intravitreal injection, patients should be examined with indirect ophthalmoscopy to assure that the optic nerve head is perfused, the retina is attached, and there is no new intraocular hemorrhage.
- g. The IOP should be measured and recorded at least 30 minutes after the intravitreal injection is administered. Monitor the IOP until it is below 30 mmHg; the subject should not be discharged until at least 30 minutes after the injection and the IOP is below 30 mmHg or at a lower level as determined by the Investigator.

After All Injections:

- 1) Zero to five minutes following intravitreal injection, patients should be examined by ophthalmoscopy to verify reperfusion of the central retinal artery in the immediate post-injection period. Verify that the retina is attached and that there is no new intraocular

hemorrhage.

[figure not shown]
- 2) After each intravitreal injection, check the IOP:
 - a. The IOP should be measured and recorded at least 30 minutes after the injection. Monitor the IOP until it is within 10 mmHg of the pre-injection value; the subject should not be discharged until at least 30 minutes after the injection and the IOP is within 10 mmHg of the pre-injection value.
 - b. If a Tono-Pen is used to check pressure, a clean Tono-Pen condom should be placed on the tip before taking each measurement. If applanation tonometry is used, the applanator tip should be cleaned as per the standard procedures of the site before using it to measure IOP. Sterile fluorescein strips and single use proparacaine bottles should be used for all patients. "Fluoracaine" or other combination fluorescein sodium and proparacaine HCl mixtures should only be used if single use presentation is available, and then only if single use bottles are available. IOP may be lowered by pharmaceutical or surgical intervention, if required. Treatment should be initiated whenever IOP is increased to the extent that the central retinal artery remains closed and the subject has no light perception for more than 1 to 2 minutes or as per Investigator judgment. Transient graying or obscuration of vision following injection, however, is expected and should not be treated. See below for additional information concerning paracentesis.
- 3) No special precautions are required before discharge of a subject who has had an uneventful recovery from the intravitreal injection(s), but patients and/or caregivers should be educated to avoid rubbing the eye and to recognize the signs and symptoms of endophthalmitis, retinal detachment and intraocular hemorrhage, including eye pain or increased discomfort, increased redness of the eye (compared to immediately after injection), blurred or decreased vision, and increased ocular sensitivity to light. Patients should be informed that some blurring of vision is common post-injection, which is often described as seeing spots floating in the eye. Patients who experience post-injection AEs that require additional monitoring should remain in the clinic for longer than 30 minutes, and treated according to the Investigator's medical judgment.
- 4) After administration, please securely discard the contents inside of the carton, flatten and retain the box for the monitor to conduct drug reconciliation.

Instructions Regarding Paracentesis:

Paracentesis should be used **only** in extreme circumstances when the degree of pressure elevation poses an imminent and irreversible threat to vision. In the rare situation when a paracentesis is warranted, the IOP should be recorded both before and after the procedure. Apply single use topical anesthetic drop(s) to the eye. Use a new pair of sterile gloves. Place a sterile lid speculum to open the eye lids. Apply 2 to 3 drops of povidone-iodine to the paracentesis site, and allow 30 to 60 seconds for the povidone-iodine to be in contact with the paracentesis site. A 0.1 mL paracentesis is performed at the temporal limbus using a 27-gauge or 30-gauge needle by the Investigator. For repeated paracentesis in the same patient, different clock-hour locations along the corneal circumference should be chosen. Further, IOP reducing drops can be applied prior to the intravitreal injection at the Investigator's discretion. Antibiotic eye drops are applied per discretion of the Investigator. Record pre- and post-paracentesis IOP measurements in the source document and on the appropriate CRF page.

NOTE: A paracentesis **MAY NOT** be performed ***prior*** to injection of the IVT drug.

